Sepsis is a life-threatening disease for which there are no effective treatments. It results from metabolic and immunologic derangements that lead to organ dysfunction, shock and sometimes death. Both "good" (high density lipoprotein, HDL-C) and "bad" (low density lipoprotein, LDL-C) cholesterol should protect against sepsis by clearing bacterial toxins from the blood and providing substrate for endogenous corticosteroids (protective in shock). However, for partially unknown reasons, cholesterol levels drop to critically low levels in early sepsis (first 48 hours), leaving the body defenseless against sepsis via these mechanisms. A fish-oil lipid injectable emulsion is FDA-approved for septic and critically ill patients that may be capable of elevating serum cholesterol levels. **We hypothesize that fish oil lipid injectable emulsion administration to critically ill septic patients will improve quantitative and qualitative lipid measures, provide substrate for bacterial toxin clearance and steroid synthesis, and lead to improvements in early organ function and mortality.** This phase II randomized pilot clinical trial, proposes to assess the drug's ability to optimally, transiently elevate cholesterol and preliminary measures of biological activity and clinical outcomes. **This novel LIPid Intensive Drug therapy for Sepsis Pilot (LIPIDS-P) clinical trial is the first study to attempt to transiently elevate cholesterol levels as a treatment modality in critically ill septic patients and will form the basis of a future Phase III randomized, controlled trial.**

1.0 Aims

Sepsis is a common, costly, and deadly condition for which there are no effective treatments. Although early interventions have improved short-term in-hospital mortality, persistent immunologic and metabolic derangements may lead to long-term organ dysfunction and late mortality.(Guirgis et al., 2014) In addition, early organ failure predicts death and subsequent chronic critical illness.(Levy et al., 2005; Shapiro et al., 2006) Novel early treatments for sepsis are needed to improve long-term outcomes.

Circulating lipoproteins play an important role in sepsis. Cholesterol plays an important role in sepsis and levels of both LDL-C and HDL-C are dynamically regulated in sepsis. Cholesterol is considered protective for its ability to bind and clear bacterial toxins, its anti-inflammatory properties, and is needed for steroid synthesis in stressful conditions. However, our research team has observed that lipid dysregulation occurs in early sepsis resulting in loss of cholesterol's protective effects. We have demonstrated in sepsis that: 1) cholesterol levels drop precipitously, and drop-severity predicts death(Guirgis, Dodani, et al., 2017); 2) low baseline LDL-C levels are associated with increased long-term community-acquired sepsis risk(Guirgis, Donnelly, et al., 2016), and 3) inflammation leads to pro-inflammatory, dysfunctional cholesterol, which predicts organ failure and adverse outcomes.(Guirgis, Dodani, et al., 2017; Guirgis, Leeuwenburgh, et al., 2017) Our research and others strongly suggest that the drastic cholesterol reduction and pro-inflammatory lipid alterations seen in early sepsis are linked to early organ failure and poor outcomes.(J.-Y. Chien, Jerng, Yu, & Yang, 2005a; Y.-F. Chien, Chen, Hsu, Chen, & Yu, 2015; Guirgis, Dodani, et al., 2017) However, it is unknown whether attempting to elevate cholesterol levels in septic patients will improve clinical outcomes.

We propose to address this gap in evidence via an interdisciplinary, multi-institution partnership (UF Health Jacksonville (UF-JAX), UF Sepsis and Critical Illness Research Center (SCIRC), & UCLA) and a pilot randomized clinical trial **LIPIDS-P** (LIPid Intensive Drug therapy for Sepsis - Pilot). A novel lipid injectable emulsion (LIE) containing 15% fish oil is FDA-approved for nutritional purposes among septic and critically ill patients and may have the ability to raise cholesterol levels and will be tested in septic patients. Furthermore, lipid therapies were recently highlighted as a top ten area for clinical testing in septic shock by thought leaders in sepsis.(Perner et al., 2017)

The rationale for this randomized clinical trial (RCT) is two-fold: (i) LIE may provide substrate for cholesterol synthesis and essential free fatty acids as metabolic fuel during septic stress, and (ii) fish oil LIE contains potent anti-inflammatory ω -3 fatty acids that have been associated with improved organ function and reduced mortality in sepsis.(Hall et al., 2015) Supporting rationale (i), a multi-center RCT of a phospholipid emulsion for gram-negative severe sepsis(Dellinger et al., 2009) initially demonstrated no effect on mortality, but when limited to patients with albumin \geq 1.5 g/dL, and cholesterol \geq 40 mg/dL or HDL-C \geq 20 mg/dL, demonstrated sepsis mortality reductions of 6.6% (p < 0.025) and 10.8% (p< 0.005), respectively.(“Parker TS,” n.d.) That study establishes that adequate liver function and a minimum quantity of cholesterol are needed for effective lipid-mediated defense against sepsis. Supporting rationale (ii), a RCT of IV 10% fish oil in 60 ICU sepsis patients showed significant improvements in organ failure (all sepsis) and improved mortality (sub-population) compared to placebo.(Hall et al., 2015) **Therefore, the central hypothesis is that fish oil LIE will improve quantitative and qualitative lipid measures, provide substrate for bacterial toxin clearance and steroid synthesis, and lead to improvements in early organ function and mortality in sepsis patients.** Our group has demonstrated access to the patient population needed for this study. In an ongoing collaborative study between UF JAX and the UF SCIRC, 120 of 223 (54%) sepsis patients met proposed enrollment criteria including total cholesterol \leq 100 mg/dL. This pilot study will gather data for a multicenter clinical trial (R01) and has the following specific aims:

Aim 1: Test if early fish oil LIE in sepsis patients will lead to achievement of 48-hour total cholesterol goals compared to controls. Recruit 48 moderate organ-failure sepsis patients with adequate liver function (albumin $>$ 1.5 mg/dL, total bilirubin $<$ 2 mg/dL) within 24h of sepsis recognition and obtain demographics, interventions, and quantitative and qualitative cholesterol measures. Because we will use the hospital's Sepsis Alert system, there may be up to 1084 subjects screened for inclusion in the study. For the Phase II trial, 48 patients will be randomized to LIE (24 patients) or active control (24 patients - no drug). Quantitative lipid measures (total cholesterol, LDL-C, HDL-C, triglycerides) will be measured (upon enrollment, 48h, 72h, and 7d after drug) to assess the ability of LIE to achieve delta total cholesterol (48-hr – enrollment) of 0 to +5 mg/dL based on preliminary data.

[figure not shown]
Aim 2: Test if sepsis patients will have a reduction in lipid oxidation measures, and improvements in HDL function, cumulative organ failure, and 28-day mortality after fish oil LIE versus controls. In 48 patients (Aim 1), the following will be collected at enrollment, 48h and 7d after enrollment: (i) lipid oxidation (cell free assay), (ii) HDL function (cholesterol efflux assay), (iii) SOFA score, and (iv) 28-day mortality.

2.0 BACKGROUND AND SIGNIFICANCE

2.1 Sepsis is common, costly, and deadly. Recent published US estimates report up to 850,000 ED sepsis visits per year(Wang, Jones, & Donnelly, 2017) costing nearly 17 billion dollars. Sepsis is also lethal, resulting in death in approximately one of every four cases and nearly 215,000 deaths per year in the US.(Angus et al., 2001)

2.2 Sepsis causes organ dysfunction which leads to chronic critical illness and death. In a prospective study of 115 sepsis patients from the UF Health Jacksonville (UF JAX) ED, 63% had organ dysfunction on admission, which was still present in 27% of survivors at 28-90 days. *Notably, in-hospital mortality was 20%, but long-term mortality was 47% at 3 years.*(Guirgis, Brakenridge, et al., 2016) The UF Sepsis and Critical Illness Research Center (P50 GM111152-02) has described chronic critical illness (CCI) in intensive care unit (ICU) patients with sepsis, characterized by ICU stays ≥ 14 days, progressive cachexia, manageable organ dysfunction, and frequent indolent death.(Gentile et al., 2012; Mira et al., 2016) Clinical trajectories were early death (12%), rapid recovery (RAP) (29%), and CCI (59%).

2.3 Preventing and limiting early organ dysfunction may prevent CCI and death. Early organ failure is strongly predictive of both progression to CCI and death.(Levy et al., 2005; Shapiro et al., 2006) SOFA score is a validated measure of organ dysfunction that directly relates to mortality(Angus et al., 2001; Shapiro et al., 2006) and is used as an endpoint in clinical trials.(Marshall et al., 2005; Vincent, 2004) Furthermore, our group has demonstrated that early SOFA elevation is predictive of persistent organ dysfunction, and that early and post-resuscitation organ failure is also highly predictive of progression to CCI.(Guirgis et al., 2014; Stortz et al., 2017)

Krohn, Meinertz, & Münzel, 2001; Rosenson et al., 2015) and iv) stimulation of endogenous corticosteroid release.(Guo et al., 2013, 2014)

2.5 Sepsis non-survivors have lower enrollment total cholesterol and LDL-C levels, which drop rapidly in the first 3 days (Figure 1). Conversely, survivors have higher baseline levels, which increase early after admission (223 UF sepsis patients). In addition, low LDL-C, total cholesterol, and HDL-C levels are associated with increased sepsis risk and poor outcomes after sepsis.(J.-Y. Chien, Jerng, Yu, & Yang, 2005b; Y.-F. Chien et al., 2015; Guirgis, Donnelly, et al., 2016; Lagrost et al., 2014; van Leeuwen et al., 2003) Decreased cholesterol levels also predict organ dysfunction and death from sepsis.(Weerapan Khovidhunkit et al., 2004)

3.0 INNOVATION AND POTENTIAL IMPACT OF RESEARCH

3.1 Enhanced reverse cholesterol transport to improve sepsis outcomes. This study will describe for the first time a potential therapy which enhances reverse cholesterol transport to clear bacterial toxins. Reverse cholesterol transport is the process by which HDL actively uptakes lower density lipids (including bound bacterial toxins) from peripheral macrophages (foam cells) and transports them to the liver for elimination. This study will test the hypothesis that lipid emulsion administration will provide a substrate for bacterial toxin

binding during sepsis and steroid synthesis leading to improved reverse cholesterol transport through the liver as well as transport of cholesterol to the adrenal glands in sepsis. (Figure 2)

3.2 Fish oil lipid injectable emulsion for sepsis. Lipid-based therapies were recently highlighted as one of the top ten areas for future clinical testing in septic shock by thought leaders in sepsis.(Perner et al., 2017)

Fish oil lipid emulsions contain anti-inflammatory long-chain ω -3 fatty acids, which may be protective in sepsis.(Li et al., 2015; Shih et al., 2016) There are four main mechanisms for these effects: i) metabolism into anti-inflammatory eicosanoid inflammatory mediators, ii) alteration of membrane lipid rafts, iii) inhibition of nuclear receptor activation (nuclear factor [NF]- κ B) to modulate production of inflammatory mediators, and, iv) metabolism into novel pro-resolving/anti-inflammatory mediators (resolvins and protectins). Exogenous administration of ω -3 may be necessary to overcome the massive inflammatory response that occurs during sepsis. A recent randomized controlled trial of 60 ICU sepsis patients demonstrated a significant improvement in organ failure after IV administration of 10% fish oil.(Hall et al., 2015)

3.3 Fish-oil lipid emulsions may safely elevate cholesterol and improve outcomes in sepsis.(D'Ascenzo et al., 2014) This may be beneficial in sepsis as increased cholesterol and phospholipids have the potential to bind and clear bacterial toxins. In addition, low cholesterol levels are associated both with poor outcomes and increased sepsis risk.(J.-Y. Chien et al., 2005a; Y.-F. Chien et al., 2015; Guirgis, Dodani, et al., 2017; Guirgis, Donnelly, et al., 2016; Guirgis, Leeuwenburgh, et al., 2017) It is not known, however, whether transiently elevating cholesterol will improve outcomes in sepsis.

[figure not shown]

[figure not shown]

With regards to adverse events (AEs), there was one patient who died within 7 days of study enrollment and two patients who died within 28 days. Other serious adverse events (SAEs) included endotracheal intubation, a below the knee amputation, chest tube placement for a pleural effusion, and emergency surgery for a misplaced gastrostomy tube. None of the SAEs were deemed to be related to study interventions. Adverse events included hyperglycemia, anemia, elevated AST, elevated triglycerides, elevated bilirubin, intravenous catheter infiltration, and elevated PT/INR values. The most common possibly related AEs included elevated liver function tests. No patients met the prespecified criteria for a dose limiting toxicity. Please see full DSM report. At the recommendation of the DSM, the Phase I study was concluded at a maximal dose of 1.6g/kg and did not proceed to 1.8 g/kg given the low likelihood of added benefit of dose escalation to 1.8g/kg body weight and feasibility issues with line infiltration given prolonged drug infusions with increasing doses. The DSM unanimously recommended proceeding to the Phase II study with the design outlined below.

4.0 APPROACH AND RESEARCH DESIGN

4.1 Design and Objectives. This is a prospective, pilot RCT of early infusion of LIE in early sepsis patients with moderate organ dysfunction (SOFA ≥ 4 with at least 2 points being new or sepsis with vasopressor dependence). The LIPIDS-P clinical trial will assess the following: 1) safety and tolerability of lipid injectable emulsion and adverse effects, 2) the drug's ability to optimally, transiently elevate cholesterol, and 3) preliminary measures of biological activity and clinical outcomes.

4.2 Study Settings, Screening and Enrollment.

A. Adult ED at UF JAX is a high volume, high acuity ED which treats approximately 80,000 patients per year. From October 2013 through November 2015 the UF JAX ED treated 2665 cases of sepsis who were admitted. The UF JAX ED is the current site of enrollment for 3 prospective sepsis research studies (one RCT) and , 3 full-time research coordinators, and 3 part-time research assistants experienced in sepsis studies, as well as a biomedical laboratory.

B. UF North ED in Jacksonville. The UF North ED is a high-volume community ED with approximately 55,000 patient volume per year. The Research Division in the Department of Emergency Medicine is capable of enrolling patients from the UF North ED.

C. Screening and Enrollment. The "Possible Sepsis" notification system as well as the Sepsis Alert systems will be used to identify patients for prospective enrollment into sepsis research studies. The "possible sepsis" notifications send hourly pages and generate a daily list of potentially septic patients throughout the hospital and is currently used by the Hospital Sepsis Taskforce. The Sepsis Alert system is activated when a patient is highly suspected of sepsis and is being managed with the hospital sepsis care bundle." For patients who meet all other inclusion and exclusion criteria a lipid panel will be obtained and added on to current lab tests to evaluate cholesterol criteria for enrollment.

D. UF Jacksonville sepsis recruitment. UF JAX Emergency Dept. patients meeting criteria will be identified by the PI and Co-I ([name]) and the research team who will be notified via pager. Prior to approaching the patient or the LAR for consent in the study, the clinical staff will approach the patient or LAR and ask them about their interest in hearing about the study. If the patient or LAR express interest, the research team will review eligibility criteria, and will seek consent. Time block sampling will be used to enroll patients between the hours of 7am and 12am, 7 days/week.⁴⁵ The team has enrolled a mean of 5 patients per month in previous studies, including [name] K23 study.

[figure not shown]

Figure 1

4.3. Enrollment Criteria.

A. Inclusion Criteria: 1) age ≥ 18 , 2) primary diagnosis of sepsis and within 24 hours of sepsis recognition and treated with institutional sepsis algorithm, 3) SOFA score ≥ 4 with at least 2 points being new or sepsis with vasopressor dependence, 4) screening total cholesterol ≤ 100 mg/dL or HDL-C + LDL-C ≤ 70 mg/dL, Screening lipids will be billed to the study.

B. Exclusion Criteria: 1) total bilirubin > 2 mg/dL, 2) serum albumin < 1.5 mg/dL, 3) hypersensitivity to fish, egg, soybean, or peanut protein, or to any of the active ingredients or excipients, 4) severe hyperlipidemia or severe disorders of lipid metabolism with serum triglycerides > 400 mg/dL, 5) alternative/confounding diagnosis causing shock or critical illness (e.g., myocardial infarction or pulmonary embolus, massive hemorrhage, trauma), 6) significant traumatic brain injury (evidence of neurologic injury on CT scan and a GCS <8), 7) refractory shock (likely death within 12 hours), 8) advanced directives restricting aggressive care or treating physician deems aggressive care unsuitable, 9) anticipated requirement for surgery that would interfere with drug infusion, 10) severe primary blood coagulation disorder, 11) acute pancreatitis accompanied by hyperlipidemia, 12) acute thromboembolic disease, 13) uncontrollable source of sepsis (e.g., irreversible disease state such as unresectable dead bowel), 14) severe immunocompromised state (e.g. subject has neutropenia receiving cytotoxic chemotherapy with absolute neutrophil count $< 500/\mu\text{L}$ or expected to decline to $< 500/\mu\text{L}$ within the next 3 days), 15) pregnancy or lactation, 16) already receiving intravenous lipid formulations (e.g., TPN, propofol, clevudine) will be excluded from the study as lipid infusion will interfere with interpretation of the study results, 17) Child Pugh Class B/C liver disease patients or liver transplant recipient ,

18) actively on extracorporeal membrane oxygenation (ECMO) or anticipated need for ECMO within 48 hours of enrollment.

4.4 Protocol. The flow diagram (**Figure 3**) represents the primary research methodology. The research team will review eligibility criteria, and will seek the appropriate consent when criteria are met. Many sepsis patients may have altered mental status or pharmacologic sedation, but would be regarded as prospective research subjects. We ask for delayed consent only for the collection of a lipid panel for these potential subjects due to the severity of the illness, the vulnerable nature of the patient at this early time point, and the challenge in reaching the patient's legal representatives. The lipid panel can frequently be added on to the patient's blood chemistry panel that nearly all septic patients already have as part of usual care. This means that it will usually not require an additional blood draw. In the unusual case that the patient does need an additional blood draw for the lipid panel, the blood will be drawn from existing venous access. For patients on whom a lipid panel is drawn prior to obtainment of written consent from the patient or LAR, we will seek written consent within 48 hours. Three attempts will be made to locate the patient or family, and each attempt will be documented in the Data Collection Forms, as well as the time, method of contact, and date. If we are unable to obtain written consent within that time period, all data will be destroyed. Only the reason for the screen failure will be recorded. Due to potential conflict of interest (patent), the PI will refrain from recruiting, and consenting patients. For fully enrolled patients, the study drug will be infused as early as practical after study enrollment and within the first 24 hours of sepsis recognition. Hours for study enrollment are based on previously completed sepsis trials. Written informed consent and written authorization will be obtained from all patients or their legal representatives prior to drug infusion in compliance with the Declaration of Helsinki and the HIPAA privacy rule. Eligible patients must be enrolled within 24 hours of sepsis recognition.

Standard of Care Treatment: All patients will be treated in the ED or in a monitored inpatient setting at UF JAX. All patients will undergo standard emergent interventions and treatment with institutional sepsis protocols, an institutional standard of care and comprised of early, evidence-based treatment of sepsis that is utilized hospital-wide. It has been shown to result in improved outcomes.(Croft et al., 2014; Guirgis, Jones, et al., 2017)

4.5 Investigational Treatment. Within 24 hours of sepsis recognition, eligible patients (or their legal representatives in the case of inability to consent) will be approached for study enrollment. If a LAR is utilized and the subject gains the capacity to consent, the subject will be re-consented. After informed consent the following study procedures will be followed:

A. Treatment. The LIE is Smoflipid (20% lipid emulsion for injection; Fresenius Kabi), which contains soybean oil, MCTs, olive oil, and fish oil in a 30:30:25:15 ratio. Smoflipid also contains 0.163 to 0.225 mg/mL of all-rac- α -tocopherol. Initial infusion rate of LIE will occur at a rate of 0.5 mL/min for the first 30 minutes. If tolerated, the infusion will proceed at the maximum FDA approved rate of 0.11g/kg/hr, and not to exceed 0.5 mL/kg/hr. The proposed dose of LIE is based on current manufacturer recommended dosing for nutritional purposes for this specific drug. The approved dose range is 1 to 2 g/kg/day, and not to exceed 2.5 g/kg/day. Since this is a pilot study, and because the lipid emulsion appears white and will be visible to the treatment team, the study will not be blinded. All infusion bags and hospital equipment that will be used for administration of LIE are standard use in the hospital and approved by the FDA, and non-PVC tubing and a 1.2 micron in-line filter will be used. All study treatments will be administered either via an existing central venous catheter or via a single lumen peripheral intravenous catheter. This approved method of administration has been shown to be safe.

B. Weight-based dosing. Dosing will be based on actual body weight in kilograms, except in cases of morbid obesity defined as actual weight (AW) > 200% ideal body weight (IBW). For morbidly obese patients, adjusted body weight (AdjBW) will be used for Smoflipid dosing according to the following formula:

$$\text{AdjBW} = \text{IBW} + 0.4(\text{ABW} - \text{IBW}).$$

Ideal body weight in (kg) will be calculated as follows.

Males: IBW = 50 kg + 2.3 kg for each inch over 5 feet.

Females: IBW = 45.5 kg + 2.3 kg for each inch over 5 feet.

C. Adverse reactions: nausea, vomiting, hyperglycemia, flatulence, pyrexia, abdominal pain, increased blood triglycerides, hypertension, sepsis, dyspepsia, urinary tract infection, anemia and device related infection, headache, sweating, dizziness, flushing, rash, urticaria, erythema, fish-like taste in mouth, coagulation defects.

4.6 Investigational Measurements.

Blood Sampling. Blood will be drawn for cholesterol levels, lipid oxidation, HDL function, inflammatory biomarkers, and SOFA score (**Appendix Table 1**). For Jacksonville subjects only, if the subject is re-admitted to the hospital for sepsis within 6 months from the index visit, we may draw an additional amount, up to 10 mL, of blood when at the time of re-admission. The additional blood draw is to assess lipid biomarkers in the subset of patients who are readmitted for sepsis and compare them to their admission baseline. These additional samples will be processed by Research Assistants in the UF Health Jacksonville Biomedical Research Laboratory and stored in the Emergency Medicine Research Data and Tissue Bank. These additional tests will be of no additional cost to the subject.

A. Cholesterol Levels. Blood will be drawn for serial lipid panels upon enrollment, then at 48 and 72h, and then at day 7. For patients discharged from the hospital prior to day 7, a phlebotomy service will be sent to the patient's place of residence (home, nursing facility, etc.) to draw their blood.

B. Lipid Oxidation. Tests of lipid oxidation including HDL inflammatory index will be performed as in current studies at UCLA using the cell free assay as in previous studies (Navab et al., 2001) after preparation at UF. This will be drawn at enrollment, at 48h, as well as 7d later to assess change over time. To prevent oxidative degradation of the samples, an antioxidant buffer will be added to samples prior to storage. (Myzak & Carr, 2002)

C. HDL Function. The cholesterol efflux assay measures the ability of HDL to move lower density lipids from peripheral macrophages to the liver for clearance. HDL-mediated cellular cholesterol efflux assays will be performed to assess potential improvements in HDL function with LIE vs. control as in previous. (Guirgis, Leeuwenburgh, et al., 2017)

D. SOFA Score. Assessment will occur at enrollment and 48h later as well as 7 days later to determine change in SOFA score over time as well as serum lactate. Necessary labs will be paid for by the study unless already ordered by the treating team.

E. Future Testing. In addition, the patient or LAR will be presented with a consent for a biobank study for future testing should they choose to participate. The biobank, Emergency Medicine Research Data and Tissue Bank, has previously been approved by the UF Jacksonville IRB and has been assigned study number IRB201601987.

Stool Sampling. A stool sample will be collected for determining lipid absorption within 24 hours of each time point when available (enrollment, 48h, 7 days) utilizing standard of care procedures by nursing and medical technicians.

4.7 Comparison Group. Phase II of this study will randomize patients to receive one of three doses of LIE or no investigational drug. The control group will receive all standard treatments mandated by the institutional Sepsis Alert protocol. For purposes of statistical outcomes analysis, the control group will be the comparison group.

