Assay	Serum (SST)	Plasma	Screen	T0		T48	T72	7 Days	28 days
Hospital Processed Labs									
Total cholesterol			■						
Hepatic function: total bilirubin and albumin			■						
Lipid Panels				■		■	■	■	
SOFA – platelet, creatinine, total bilirubin (if SOC labs not available for SOFA calculation)				■		■		■	
Research Processed Labs and Procedures									
Lipid absorption (from stool samples)				■		■		■	

Lipid oxidation and HDL function	■			■		■		■	
Phone follow up									■

Table 2. Sequential Organ Failure Assessment Score.

SOFA Score	0	1	2	3	4
Respiratory PaO ₂ /FiO ₂ SpO ₂ /FiO ₂	>400 >302	<400 <302	<300 <221	<200 <142	<100 <67
Cardiovascular	MAP \geq 70 mm Hg	MAP \leq 70 mm Hg	Dopamine \leq 5 or ANY Dobutamine	Dopamine >5 or Norepinephrine \leq 0.1 Phenylephrine \leq 0.8	Dopamine >15 or Norepinephrine >0.1 Phenylephrine >0.8 ANY Vasopressin
Liver Function Bilirubin, mg/dL	< 1.2	1.2-1.9	2.0-5.9	6.0-11.9	> 12
Renal Creatinine, mg/dL	< 1.2	1.2-1.9	2.0-3.4	3.5-4.9	>5.0
Coagulation Platelets \times 10 _{3/mm³}	\geq 150	<150	< 100	<50	<20
Neurologic GCS	15	13-14	10-12	6-9	<6

References

Angus, D. C., Linde-Zwirble, W. T., Lidicker, J., Clermont, G., Carcillo, J., & Pinsky, M. R. (2001). Epidemiology of severe sepsis in the United States: analysis of incidence, outcome, and associated costs of care. *Critical Care Medicine*, 29(7), 1303–1310.

Boyd, J. H., Fjell, C. D., Russell, J. A., Sironis, D., Cirstea, M. S., & Walley, K. R. (2016). Increased Plasma PCSK9 Levels Are Associated with Reduced Endotoxin Clearance and the Development of Acute Organ Failures during Sepsis. *Journal of Innate Immunity*, 8(2), 211–220. <https://doi.org/10.1159/000442976>

Catapano, A. L., Pirillo, A., Bonacina, F., & Norata, G. D. (2014). HDL in innate and adaptive immunity. *Cardiovascular Research*. <https://doi.org/cvu150> [pii]

Chien, J.-Y., Jerng, J.-S., Yu, C.-J., & Yang, P.-C. (2005a). Low serum level of high-density lipoprotein cholesterol is a poor prognostic factor for severe sepsis. *Critical Care Medicine*, 33(8), 1688–1693. Retrieved from <http://www.ncbi.nlm.nih.gov/pubmed/16096442>

Chien, J.-Y., Jerng, J.-S., Yu, C.-J., & Yang, P.-C. (2005b). Low serum level of high-density lipoprotein cholesterol is a poor prognostic factor for severe sepsis. *Critical Care Medicine*, 33(8), 1688–1693. <https://doi.org/10.1097/01.CCM.0000171183.79525.6B>

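### The albumin cut-off is 1.5 mg/dL in exclusion 2 and Aim 1 but 1.5 g/dL in the rationale; read literally, exclusion 2 excludes no plausible patient

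*Combined protocol and SAP*

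**What the plan says.** Three places in the protocol give an albumin limit of 1.5.

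- **Section 4.3 B, Exclusion Criteria, item 2**, the operative eligibility list, excludes patients with "serum albumin < 1.5 mg/dL".
- **Section 1.0, Aim 1**, a summary of the population, describes patients with "adequate liver function (albumin $>$ 1.5 mg/dL, total bilirubin $<$ 2 mg/dL".
- **Section 1.0, rationale**, describes a result from an earlier trial of a phospholipid emulsion when the analysis was "limited to patients with albumin \geq 1.5 g/dL" and to patients meeting lipid minimums. It then concludes: "That study establishes that adequate liver function and a minimum quantity of cholesterol are needed for effective lipid-mediated defense against sepsis".

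Albumin is a screening test. Table 1, Schedule of Events, lists "Hepatic function: total bilirubin and albumin" in the screening column without a unit. No part of the protocol states this trial's own albumin cut-off in g/dL, and none reconciles the two units.

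**The concern.** The number is the same in all three places, but the unit changes between the rationale and the criterion. An eligibility limit is a decision rule: it determines who is randomized, and a monitor can audit against it. If the limit lies far below any value a patient could have, the rule does no work, although the protocol lists it separately and presents adequate liver function as a condition for the mechanism it wants to test.

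Two things would be at stake if the criterion were applied as written. Patients whom the rationale suggests were not meant to be in the trial could enter it. The groups are small (24 per arm, and 4 per dose in the first 24 patients), so even one or two such patients could weigh on the choice of doses. An audit would also have no clear standard. A patient with an albumin of 1.2 g/dL (an illustrative value) is eligible under the written unit and would be excluded under the unit in the rationale. The protocol is also meant to form the basis of a Phase III trial, so the discrepancy could be carried forward.

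**Working it through.** The cut-off is stated and not calculated, so there is no figure of the plan to reproduce. The check is a unit conversion followed by applying the rule.

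**Inputs**

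- Written limit, Section 4.3 B item 2: exclude if albumin is below 1.5 mg/dL.
- Aim 1: include if albumin is above 1.5 mg/dL.
- Rationale, Section 1.0: at least 1.5 g/dL.
- Albumin values to test: the documents give no distribution, so I assume a range of 0.5 to 3.5 g/dL.

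**Conversion.** 1 g = 1000 mg, so 1.5 mg/dL = 1.5 / 1000 = 0.0015 g/dL. The ratio of the two limits is 1.5 / 0.0015 = 1000.

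**Applying the rule**

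| Assumed albumin (g/dL) | In mg/dL | Excluded as written (below 1.5 mg/dL)? | Excluded if the unit were that of the rationale (below 1.5 g/dL)? |
|---|---|---|---|
| 0.5 | 500 | no | yes |
| 1.0 | 1000 | no | yes |
| 1.4 | 1400 | no | yes |
| 1.5 | 1500 | no | no |
| 2.0 | 2000 | no | no |
| 3.5 | 3500 | no | no |

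As written, the rule excludes none of the six values; in the other unit it would exclude three. The lowest value tested is 500 / 1.5 = 333 times the written limit. The result does not depend on the range chosen: any albumin at or above 0.0015 g/dL passes.

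**Boundary.** An albumin of exactly 1.5, in either unit, fails Aim 1, which requires a value strictly above 1.5. Section 4.3 does not exclude it, because it removes only values strictly below 1.5. The two statements therefore disagree at that value whatever the unit.

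**What is not affected.** Albumin does not enter the sample-size calculation. With 24 per arm, SD 23 and a two-sided t-test at 0.05, a difference of 17 mg/dL in cholesterol gives 70.8% power and 19 mg/dL gives 80.0%. These match the stated 71% and 80%.

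**The case against.** The best case on the other side is that this is a unit slip that any clinician would see through. Since every plausible patient exceeds 1.5 mg/dL, the written limit looks wrong at once, and the matching number in the rationale suggests how it arose. In both places the albumin limit stands next to a bilirubin limit in mg/dL, so the unit may simply have been carried across. Section 4.9 I has case report forms completed by trained coordinators with a clinical degree and makes a named role responsible for checking eligibility. No eligibility form or programmed check in mg/dL appears in the documents. If staff read g/dL, nothing happens.

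Most of that stands, and it limits the point. Three stronger readings are tempting but not supported:

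- **That unintended patients were or will be enrolled.** This requires someone to apply the limit literally, and the documents do not show that anyone does. The number of patients affected cannot be estimated without an albumin distribution.
- **That the trial has no screen for liver function.** Exclusion 1 (total bilirubin above 2 mg/dL) and exclusion 17 (Child Pugh B/C disease or liver transplant) still apply. Only patients who pass both and have low albumin are in question.
- **That the protocol says its limit was taken from the earlier trial.** It does not. The link is an inference from the identical number and the shared idea of adequate liver function. The rationale also speaks of lipid-mediated defense in general and cites a different emulsion.

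The repetition in Aim 1 does not make the case twice as strong, since Aim 1 is a summary and only Section 4.3 is the operative list. It does make a fault in reading the PDF unlikely.

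What the objection does not remove is that the operative criterion, as written, cannot be enforced. The safeguards described concern who checks eligibility; none of them states the albumin unit.

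**Conclusion.** The inconsistency is real and lies within the protocol. Section 4.3 and Aim 1 give 1.5 mg/dL, the rationale gives 1.5 g/dL, and the two differ by a factor of 1000. Read literally, exclusion 2 excludes no plausible patient. The only assumption behind that statement is that no patient has an albumin below 0.0015 g/dL.

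The effect on enrollment ranges from nil, if staff read the limit in g/dL, to the loss of the albumin screen, if the text is applied as it stands. In the second case the bilirubin and Child Pugh exclusions remain. The fault is in the wording and enforceability of one criterion. It is not evidence of wrong enrollment, and it does not touch the power, the randomization, the primary endpoint or the analysis. It merits correction because it sits in the eligibility list, where text is followed and audited.

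**What to change.** The sponsor should:

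1. Reconcile the albumin unit across the rationale in Section 1.0, Aim 1 and exclusion 2 in Section 4.3. Which limit applies is the sponsor's clinical decision.
2. Settle the boundary so that Aim 1 and Section 4.3 treat a value of exactly 1.5 in the same way.
3. Print the reconciled limit and unit on the eligibility form, and add the unit to the screening row of Table 1.

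The cost is a few words in the next amendment and a check that the form agrees. No change to the design, sample size or analysis follows. If patients have already been enrolled, comparing their recorded screening albumin with the reconciled limit would show whether the question ever arose in practice.
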